STUDY PROTOCOL & STATISTICAL ANALYSIS PLAN

Official Title:	HYPERTHERMIA AS AN ADDITIONAL TREATMENT FOR THE BIOLOGY AND EXPERIENCE OF DEPRESSION: THE HEATBED STUDY
Clinicaltrials.gov #	NCT05708976
Date	25 September 2025
Development Phase:	Feasibility & Acceptability
Sponsor:	[name] & [name] UCSF Osher Center for Integrative Health School of Medicine [name]
Principal Investigator:	Name: [name] E-mail: [contact]
Co-Principal Investigator	Name: [name] E-mail: [contact]

BACKGROUND

Depression recovery is not uniformly linear; people who recover from depression often experience acute improvements, termed ‘sudden gains,’ early in treatment. Data suggest that participants with clinical depression who receive whole body heating (Hanusch et al., 2013; Janssen et al., 2016) and participants who receive cognitive behavioral therapy (CBT) treatment (Aderka et al., 2012; Tang et al., 1999) show sudden gains. Ascertaining if a treatment comprising both sauna sessions and CBT sessions is feasible and tolerable will allow for further research of this integrative mind-body treatment as a potentially effective and disseminable treatment for clinical depression.

Prior work has demonstrated that whole body heating to an internal temperature of 38.5 °C (101.3 °F) using a head out infrared heating device is tolerable by healthy adults and is associated with significant reductions in clinical depression (Hanusch et al., 2013; Janssen et al., 2016) that characterize sudden gains. This prior work administered a single sauna session in a Heckel heating device, a medical hyperthermia device, and reported improvements in depression symptoms within 1 week of this session. This prior work did not ascertain if additional sauna sessions led to further decreases in depression; a dose-escalation study has not yet been performed. Our earlier pilot project established (in $N=25$ participants) that a readily accessible, commercially available sauna, which the UCSF IRB granted NSR designation, can achieve a core temperature of 101.3 °F without serious adverse events.

In addition to the body-based approach of using sauna as a possible treatment for depression symptoms, we will provide the current gold standard psychotherapy intervention, cognitive behavioral therapy (CBT) to participants. Cognitive behavioral therapy (CBT) is an efficacious, highly disseminable evidence-based treatment for depression. Many therapy modalities can elicit sudden gains; however, *sudden gains in cognitive behavioral therapy (CBT) are more frequent and durable* than those observed in non-CBT therapies (Aderka et al., 2012). Meta-analytic data suggest that the effects of sudden gains on depression symptoms in the context of CBT treatment are larger (Hedges's $g=0.74$) and longer lasting than those occurring in the context of non-CBT treatment (Hedges's $g=0.23$; Aderka et al., 2012). The conceptual framework of sudden gains suggests that such gains can lead to cognitive changes that then lead to further symptom reduction, sparking a positive feedback loop termed an “upward spiral” (Tang & DeRubeis, 1999). Sudden gains in CBT generally follow from “critical” therapy sessions characterized by substantial cognitive change. CBT is an effective manualized psychotherapy that a diverse range of mental health clinicians, including marriage and family therapists (MFTs) and clinical social workers (CSWs), can provide. In many areas, MFTs and CSWs are more readily available and affordable than clinical psychologists. Hence, optimizing an intervention that includes a psychotherapy modality that a range of mental health clinicians can provide strengthens the potential for dissemination.

References:

- Hanusch, K.-U., Janssen, C. H., Billheimer, D., Jenkins, I., Spurgeon, E., Lowry, C. A., & Raison, C. L. (2013). Whole-body hyperthermia for the treatment of major depression: Associations with thermoregulatory cooling. *American Journal of Psychiatry*, 170(7), 802–804.
- Janssen, C. W., Lowry, C. A., Mehl, M. R., Allen, J. J. B., Kelly, K. L., Gartner, D. E., ... Raison, C. L. (2016). Whole-Body Hyperthermia for the Treatment of Major Depressive Disorder: A Randomized Clinical Trial. *JAMA Psychiatry*, 73(8), 789–795.

TITLE	EXAMINING THE FEASIBILITY AND ACCEPTABILITY OF SAUNA SESSIONS AND COGNITIVE BEHAVIORAL THERAPY (CBT) FOR PARTICIPANTS WITH CLINICAL DEPRESSION
SPONSOR	[name]
CO-SPONSOR	[name]
NUMBER OF SITES	1
RATIONALE	Depression recovery is not uniformly linear; people who recover from depression often experience acute improvements, termed ‘sudden gains,’ early in treatment. Data suggest that participants with clinical depression who receive whole body heating (Hanusch et al., 2013; Janssen et al., 2016) and participants who receive cognitive behavioral therapy (CBT) treatment (Aderka et al., 2012; Tang et al., 1999) show sudden gains. Ascertaining if a treatment comprising both sauna sessions and CBT sessions is feasible and tolerable will allow for further research of this integrative mind-body treatment as a potentially effective and disseminable treatment for clinical depression.
STUDY DESIGN	Randomized, blinded pilot trial

PRIMARY OBJECTIVE	Pilot RCT procedures: We will conduct a pilot trial ($N=30$) to test the feasibility and acceptability of recruitment, retention, and randomization procedures in preparation for a larger efficacy trial of WBH+CBT. We will randomize participants with clinical depression to receive 8 weekly CBT + 4 biweekly active sauna sessions (refined during Aim 1) or 8 weekly CBT + 4 biweekly sham sauna sessions. After the first half of enrollment ($n=15$) is complete, we will use participant and staff feedback to refine procedures for the remaining enrollment (we will submit any refinements or changes to the treatment to the UCSF IRB approval before implementing them).
SECONDARY OBJECTIVES	To pilot test the feasibility of all assessment procedures in anticipation of a larger trial.
NUMBER OF PARTICIPANTS	30
PARTICIPANT SELECTION CRITERIA	
Inclusion Criteria:
 
 1. Age of at least 18 years old 2. Current major depressive episode of at least 2 weeks duration as assessed by the Structured Clinical Interview for DSM-5 (SCID) and a Beck Depression Inventory-II (BDI-II) score ≥ 21 at screening 3. Able to understand the nature of the study and able to provide written informed consent prior to conduct of any study procedures 4. Must have smartphone onto which they can download an app from Apple App or Google Play stores 5. Ability to lie supine (on back) for 2 hours (required for sauna sessions) 6. Must be fully vaccinated against COVID-19 
Exclusion Criteria:
 
 1. $>30\%$ reduction in BDI-II score between Screen #1 and Screen #2 (conducted ~ 1 week after Screen #1). 2. Suicide attempt in the past 12 months defined using the SAMHSA suicidality question during the clinician-administered interview or active suicidal ideation as indexed by a score of 3 on the BDI-II suicidality item during the clinician-administered interview. 3. Any of the following medical conditions: cardiovascular disease (other than controlled hypertension), seizure disorder, history of cerebrovascular accident (CVA) or other serious neurological condition (e.g. Parkinson's disease, multiple sclerosis, or dementia), current neoplasia, any active enclosed infection (e.g. dental abscess, joint infection), hemophilia or other cause for excessive bleeding (e.g. platelet disorder), or other medical

	
condition that in the opinion of investigators may increase the risk of WBH
 
 4. Comorbid psychiatric conditions or history of comorbid psychiatric conditions that might better explain depressive symptoms, including schizophrenia, schizoaffective disorder, Bipolar Disorder I, Obsessive Compulsive Disorder, Anorexia Nervosa, Bulimia Nervosa, Alcohol Dependence, or Drug Dependence 5. Known hypersensitivity to hyperthermia and/or infrared exposure 6. Inability to fit into the sauna device 7. Breast implants 8. Pregnancy, active lactation or intention to become pregnant during the study period 9. Use of any medication that might impact thermoregulatory capacity, including: 
 • diuretics, barbiturates • beta-blockers • antipsychotic agents • anti-cholinergic agents or chronic use of antihistamines • aspirin (other than low-dose ASA for prophylactic purposes) • medication prescribed for the treatment of depression (antidepressant medication [ADM]) including but not limited to: selective serotonin reuptake inhibitors [SSRIs], Serotonin and norepinephrine reuptake inhibitors [SNRIs], Monoamine oxidase inhibitors [MAOIs], Tricyclics [TCAs], and atypical antipsychotic and antidepressant medications (participants must have been free of these medications for at least 4 weeks) • antibiotics (past 14 days), pain medication (opioids) due to procedure, e.g., dental procedure (past 14 days), Emergency contraception pill (past 14 days) • any other medication that in the judgment of the PI would increase risk of study participation or introduce excessive variance into physiological or behavioral responses to WBH • recent use (multiple consecutive doses) of: non-steroidal anti-inflammatory drugs (NSAIDs), systemic corticosteroids, cytokine antagonists 10. Regular use of any nicotine products, including cigarettes, vapes, chewing tobacco, or other forms of nicotine (if use is not regular, must be willing to refrain for 24 hours before and 24 hours after sauna session) 11. Unwilling to refrain from using marijuana products and alcohol for the 24 hours before and 24 hours after sauna sessions
--	-------------------------------------------------------------------------------------------------------------------------------------------------------------------------------------------------------------------------------------------------------------------------------------------------------------------------------------------------------------------------------------------------------------------------------------------------------------------------------------------------------------------------------------------------------------------------------------------------------------------------------------------------------------------------------------------------------------------------------------------------------------------------------------------------------------------------------------------------------------------------------------------------------------------------------------------------------------------------------------------------------------------------------------------------------------------------------------------------------------------------------------------------------------------------------------------------------------------------------------------------------------------------------------------------------------------------------------------------------------------------------------------------------------------------------------------------------------------------------------------------------------------------------------------------------------------------------------------------------------------------------------------------------------------------------------------------------------------------------------------------------------------------------------------------------------------------------------------------------------------------------------------------------------------------------------------------------------------------------------------------------------------------------------------------------------------------------------------------------------------------------------------------------------------------------------------------------------------------------------------------------------------------------------------------------------------------------------------------------------------------------------------------------------------------------------------

	
12. Unwilling to refrain from heavy exercise on the day of sauna sessions
 
13. Unwilling to refrain from engaging with sauna, hot yoga, cold plunges, cryotherapy, and hot tub/jacuzzi outside of study (prospective participant must not have engaged with any of these activities for 30 days prior to their baseline study visit).
 
14. Has begun new psychotherapy treatment in the prior 6 weeks
 
*Note: All medications reported by potential subjects will be reviewed by medical monitor [name]. If the medication is determined to not have meaningful impacts on bodily thermoregulatory processes and to not interact with whole body heating, the subject may participate.

TEST PRODUCT, DOSE, AND ROUTE OF ADMINISTRATION	Portable Sauna Dome – One Person Supine sauna device, head out, body inside of sauna Sauna session approx. 80 – 140 minutes, maximum 140 minutes Manufactured by Clearlight Infrared
CONTROL PRODUCT, DOSE AND ROUTE OF ADMINISTRATION	All participants receive cognitive behavioral therapy (CBT), and 50% of participants receive active sauna sessions while 50% receive sham sauna sessions (the test product treatment listed above, Portable Sauna Dome)
DURATION OF PARTICIPANT PARTICIPATION AND DURATION OF STUDY	
This is a single-center, two-arm, randomized experimental study that will include 30 participants. Participants will be in the study for approximately 10 weeks. Total time involved will be approximately ~34 hours:
 
 • E-Screen: Web-based eligibility screen for self-report eligibility criteria 
 ○ ~10 minutes • Phone Screen: Phone call to review eligibility, verify shipping address for Oura ring sizing kit and schedule baseline study visits 
 ○ ~25 minutes • In-Person Screen / Baseline Visit: Participant to complete screening procedures, provide informed written consent and receive bill of rights, download Oura ring app, complete self-report questionnaires, anthropometric assessments, schedule study visits. Randomization to receive either active sauna sessions or sham sauna sessions. 
 ○ ~220 minutes • Weekly depression survey: Web-based surveys assessing depression symptoms on Mondays. 
 ○ ~ 10 minutes each

	
 • Sauna Visits 1-4: In-person visits, participant (if female) to complete pregnancy screen if the participant thinks there is a possibility of pregnancy, COVID-19 rapid test, complete questionnaires (all sauna visits), provide saliva samples (Sauna Visits 1 and 4) and blood samples (Sauna Visit 1, Sauna Visit 4 if the participant chooses), and complete sauna session 
 ○ ~220-240 minutes each • Cognitive Behavioral Therapy (CBT) Visits 1-8: In-person visits, participant to receive 50-minute CBT session and complete self-report measures 
 ○ ~65 minutes each • Closeout Visit: In-person visit, participant to complete questionnaires, complete clinician-administered assessment, provide blood and saliva samples, and return Oura ring. 
 ○ ~60 minutes
CONCOMMITANT MEDICATIONS	
Allowed:
 
 • All medications reported by potential participants will be reviewed by medical monitor [name]. If the medication is determined to not have meaningful impacts on bodily thermoregulatory processes and to not interact with whole body heating, the participant may participate. 
Prohibited:
 
 1. Use of any medication that might impact thermoregulatory capacity, including: diuretics, barbiturates, beta-blockers, antipsychotic agents, anti-cholinergic agents or chronic use of antihistamines, cytokine antagonists 2. Current antidepressant medications (all classes) or use within the past 30 days 3. Recent use (multiple consecutive doses) of systemic corticosteroids 4. Needing to use antihistamines, aspirin (other than low-dose ASA for prophylactic purposes), non-steroidal anti-inflammatory drugs (NSAIDs), or systemic corticosteroids, on Study Visit days 5. Use of any other medication that in the judgment of the PI would increase risk of study participation or introduce excessive variance into physiological or behavioral responses to WBH 6. Regular use of any nicotine products, including cigarettes, vapes, chewing tobacco, or other forms of nicotine 7. The following medications in these timeframes: Antibiotics (past 14 days), Pain medication (opioids) due to procedure, e.g., dental procedure (past 14 days), Emergency contraception pill (past 14 days)

EFFICACY EVALUATIONS	See below for primary and secondary endpoints.
PRIMARY ENDPOINT	Primary outcomes. The primary endpoint is study acceptability, as indexed by participant-reported net-promoter scores, which will range from 0 (would not recommend) to 10 (would definitely recommend).
SECONDARY ENDPOINTS	Secondary outcomes. We will assess pre-post intervention changes in: Beck Depression Inventory (BDI-II), Patient-Reported Outcome Measurement System (PROMIS) Depression, PROMIS Anxiety, and the Hamilton Depression Rating Scale (HAMD-6).
OTHER EVALUATIONS	N/A
SAFETY EVALUATIONS	Incidence of unexpected adverse events. We will monitor participants for unexpected adverse events and serious adverse events during and following the sauna sessions.
PLANNED INTERIM ANALYSES	Due to the current study design and safety profile of this test product (portable sauna dome – one person) and cognitive behavioral therapy (CBT; a standard depression psychotherapy treatment), we do not plan any interim analyses.
STATISTICS Primary Analysis Plan	
Primary outcome: We assessed study acceptability by computing means and standard deviations of participant-reported net-promoter scores, which will range from 0 (would not recommend) to 10 (would definitely recommend).
 
Note on Original Primary Outcome: Although we collected and reported this outcome, participants noted that they may not have recommended the study as highly to others because antidepressant medication use was an exclusion criteria, and many participants knew that their friends or family members used these medications. Because that awareness may have biased net promotor scores downward, we report an additional acceptability measure.
 
Revised Additional Primary Outcome: A second study acceptability measure asked participants how likely they would be to enroll in the study given their experience in the study, on a scale from 1 (extremely unlikely to enroll) to 5 (extremely likely to enroll). We reported the score mean and standard deviation.
 
Secondary outcomes: We assessed change in scores on the Beck Depression Inventory (BDI-II), Patient-Reported Outcomes Measurement Information Systems (PROMIS) measures, and Hamilton Depression Rating Scale (HAMD-6), using T-Tests, and report the mean changes and associated standard errors. Units for PROMIS measures are T-Score points.

Rationale for Number of Participants	The primary endpoint is participant-reported net-promoter scores, which will range from 0 (would not recommend) to 10 (would definitely recommend). If 25 of 30 Aim 2 participants rate the study experience > 7 (83%), the 95% CI will be 70% to 97% (normal approximation to the binomial), which we also believe will provide

	adequate precision for feasibility/acceptability testing.
--	-----------------------------------------------------------

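### Depression is surveyed weekly, but it is analysed only by unadjusted t-tests on pre-post change, with no missing-data rule and no use of the weekly scores

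*Combined protocol and SAP*

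**What the plan says.** Under Duration of Participant Participation, the plan describes a "single-center, two-arm, randomized experimental study that will include 30 participants", split equally between active and sham sauna. It adds that "Participants will be in the study for approximately 10 weeks". The same list includes a weekly depression survey: "Web-based surveys assessing depression symptoms on Mondays". Neither the instrument nor the number of surveys is given. At CBT visits 1-8 the "participant to receive 50-minute CBT session and complete self-report measures", again without naming the measures. At closeout the plan has the "participant to complete questionnaires, complete clinician-administered assessment, provide blood and saliva samples, and return Oura ring".

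Secondary Endpoints reads "We will assess pre-post intervention changes in" four scales: BDI-II, PROMIS Depression, PROMIS Anxiety and HAMD-6. The Statistics section analyses change in these scores "using T-Tests, and report the mean changes and associated standard errors".

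The documents do not state:
- whether the t-tests are paired or compare the arms;
- which visit supplies the post score;
- a missing-data rule or an analysis set;
- any analysis of the weekly survey.

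**The concern.** A change-score t-test needs two scores per person. With no rule for missing scores, anyone without a post score is left out by default, even with several weekly scores on file. Retention is one of the things this pilot tests, so drop-out is a real possibility. If those who leave are the ones not improving, and more leave one arm than the other, a comparison of completers is biased.

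The t-test on change also forgoes the precision that baseline adjustment would give.

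Finally, the rationale rests on sudden gains, meaning early and abrupt improvement. A two-point change cannot show when improvement happened; weekly scores can.

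**Working it through.** **Inputs.** From the documents: 30 participants, half to each arm, so 15 per arm; about 10 weeks; one depression survey a week. Assumed: the number of scores (9 or 10), SD, correlations, true difference, drop-out, and that the t-test compares the arms.

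**The plan's own figure.** The only precision figure is in Rationale for Number of Participants and concerns acceptability. 25/30 = 0.833; half-width 1.96 × √(0.833 × 0.167/30) = 0.133; interval 70.0% to 96.7%. This reproduces the stated 70% to 97%. No precision or power figure is given for depression.

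**Step 1: cost of missing post scores.** If a fraction d is missing at random, the standard error (SE) grows by 1/√(1 − d):
- d = 10%: 27 of 30 remain, SE up 5%
- d = 20%: 24 remain, SE up 12%
- d = 30%: 21 remain, SE up 20%

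**Step 2: source of the precision gain.** Let r be the baseline-to-final correlation and n the number per arm. In SD units:
- t-test on change: SE = √(4(1 − r)/n)
- ANCOVA: SE = √(2(1 − r²)/n)
- variance ratio, ANCOVA to t-test: (1 + r)/2

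For r = 0.5 and n = 15: √(2/15) = 0.365 against √(1.5/15) = 0.316, a ratio of 0.75.

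The repeated-measures model below has 10 occasions, a common baseline, known covariance and random drop-out spread evenly over the weeks.

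| Correlation | Drop-out | t-test SE | ANCOVA SE | Model SE | ANCOVA/t variance | Model/t variance |
|---|---|---|---|---|---|---|
| Exchangeable 0.5 | 0% | 0.365 | 0.316 | 0.316 | 0.75 | 0.75 |
| Exchangeable 0.5 | 20% | 0.408 | 0.354 | 0.346 | 0.75 | 0.72 |
| AR(1) 0.9 | 0% | 0.404 | 0.337 | 0.337 | 0.69 | 0.69 |
| AR(1) 0.9 | 30% | 0.483 | 0.402 | 0.381 | 0.69 | 0.62 |

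Over exchangeable correlations of 0.3-0.7, AR(1) of 0.8-0.9 and drop-out of 0-30%, the ANCOVA ratio is 0.57-0.85 and the model ratio 0.53-0.85. A simulation with covariance estimated by REML and complete data agrees (on the scale where the true difference is -4): ANCOVA SE 3.1-3.4, model SE 3.1-3.3. So with complete data nearly all of the final-week gain comes from baseline adjustment.

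**Step 3: bias under informative drop-out.** Simulations used 15 per arm, a true final difference of -4, and drop-out in the active arm only, driven by poor response already observed.

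| Scenario | t-test | Completers' ANCOVA | Model |
|---|---|---|---|
| 9 scores, SD 10, about 14-16% drop-out, covariance known | -4.8 to -5.6 | not run | -3.95 to -3.98 |
| 9 scores, SD 10, 16-20% drop-out overall, covariance known | -7.5 to -8.2 | -5.9 to -6.4 | -3.9 to -4.2 |
| Covariance estimated by REML | -5.2 to -6.4 | -4.8 to -5.5 | -3.8 to -4.3 |

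In the REML row the t-test overstates the effect by 1.2 to 2.4 points (30-60% of 4) and ANCOVA by 0.8 to 1.5 (20-38%). The model is within 0.3 of the truth, with interval coverage of 94-99%. ANCOVA reduces this bias; the weekly scores remove most of what is left.

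**The case against.** **Precision.** It is tempting to say that using every weekly score makes the final comparison more precise. Step 2 does not support that for complete data: a two-point ANCOVA does as well. The objection stands, and the precision argument belongs to baseline adjustment.

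**The drop-out scenario was chosen.** It is one-sided and depends on observed scores, which is the missing-at-random case a likelihood model is built to handle. The documents give no drop-out figure. This also stands: the bias figures show what can happen, not what is expected, and the model offers no such protection if leaving depends on unobserved scores. Estimating the covariance, however, did not undo the result.

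**What the documents do not say.** A reader might infer that the plan excludes participants without a closeout score. It does not say so, nor that closeout supplies the post score; exclusion is only the default when no rule is given. A reader might also infer that most of the depression data are discarded. That can apply only to the weekly survey. Nothing shows that HAMD-6 or PROMIS Anxiety is collected weekly, and with the instrument unnamed it cannot be confirmed that BDI-II or PROMIS Depression is.

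**Timing and weight.** The Statistics section is largely in the past tense, so results may already be known. This is a feasibility pilot sized on acceptability, with no power claimed for depression. Both points limit the weight of the finding; neither removes it.

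**Conclusion.** The concern holds in a limited form. The planned depression analysis is an unadjusted change-score t-test that ignores the weekly survey and, by default, omits anyone without a post score. Baseline adjustment alone would reduce the variance of the arm difference by 15-43% (1 − 0.85 to 1 − 0.57). The weekly scores add little precision at the last week, but they protect against bias when drop-out depends on scores already observed. In the REML scenario they bring the estimate from -5.2 to -6.4 (t-test) back to -3.8 to -4.3 against a truth of -4.

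These sizes rest on assumed correlations, drop-out and number of surveys, and on a t-test that compares arms. The change is worth making, but it does not affect the trial's primary acceptability question.

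**What to change.** 1. Name the Monday instrument, the number of surveys and the visit that supplies the post score. State the t-test contrast, the analysis set and a missing-data rule.
2. For any scale measured at two visits only, compare the arms by ANCOVA on baseline with a confidence interval, beside the t-test.
3. For the scale the Monday survey carries, if it is also measured at baseline, add a repeated-measures model using all weekly scores from all randomised participants. Use a common baseline, arm-by-week terms, a parsimonious covariance (for example random intercept plus AR(1)) and small-sample degrees of freedom. Report the arm difference at the last week with a confidence interval.
4. If that scale is not one of the four named secondary outcomes, label the model exploratory. If results have already been seen, label it post hoc and report it beside the planned t-test, not in its place.

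The cost is plan wording and modest programming, since the survey is already scheduled. The downside is reliance on a covariance model and a missing-at-random assumption with only 30 participants.

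### Pregnancy is an exclusion, but the only pregnancy screen described depends on the participant's own judgement, so an unrecognised pregnancy can go undetected

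*Combined protocol and SAP*

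**What the plan says.** Under Participant Selection Criteria, exclusion 8 reads "Pregnancy, active lactation or intention to become pregnant during the study period". It is not limited to pregnancies the participant knows about. The age criterion is "Age of at least 18 years old", and no criterion restricts entry by sex or childbearing potential.

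The section on duration of participation lists three steps before the first sauna visit:

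- E-Screen: "Web-based eligibility screen for self-report eligibility criteria".
- Phone Screen: "Phone call to review eligibility, verify shipping address for Oura ring sizing kit and schedule baseline study visits".
- In-Person Screen / Baseline Visit: "Participant to complete screening procedures, provide informed written consent and receive bill of rights", followed by "download Oura ring app, complete self-report questionnaires, anthropometric assessments, schedule study visits". Randomization takes place at this visit.

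The entry for Sauna Visits 1-4 contains the only pregnancy screen in the documents: "participant (if female) to complete pregnancy screen if the participant thinks there is a possibility of pregnancy". The same entry lists a rapid COVID-19 test with no such condition, and a blood sample at Sauna Visit 1 with no pregnancy assay mentioned.

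On allocation, the control-product section states that "50% of participants receive active sauna sessions while 50% receive sham sauna sessions".

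**The concern.** Self-report at the E-Screen and Phone Screen can already remove a woman who knows she is pregnant. A screen adds most for a woman who does not know. The sauna-visit rule makes the screen depend on her own assessment, so it is skipped when that assessment is wrong in the direction that matters.

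Two things are at stake. The first is safety: the protocol itself treats pregnancy as incompatible with participation, and the active intervention is whole-body heating. The second is that this pilot exists to test procedures for a larger efficacy trial. An exclusion with no stated means of verification would carry forward into that trial. No sample size, precision or analysis figure is affected.

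**Working it through.** The plan gives no figure to reproduce on this point. The check sets criterion 8 against each step at which it could be enforced.

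| Step | Before randomization? | Pregnancy check named? | Depends on participant's own view? |
|---|---|---|---|
| E-Screen | Yes | No | Yes, self-report |
| Phone Screen | Yes | No | Yes, as far as described |
| In-Person Screen / Baseline Visit | Yes | No; screening procedures not itemised | Not stated |
| Sauna Visits 1-4 | No | Yes | Yes, by the stated condition |

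No row combines a named check with independence from the participant's judgement. There are therefore two separate gaps. At eligibility, no check is named. Before each session, a check is named but is conditional.

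The path through the plan is then as follows. A participant who is pregnant, does not know it and sees no possibility of it answers truthfully at every step. No described procedure detects the pregnancy, so she can be randomized and can attend the sauna sessions.

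Exposure, from the plan's figures:

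- Participants allocated to active heating: 50% of 30 = 15.
- Sessions per participant: 4. Reading biweekly as every two weeks (8 weekly CBT sessions run alongside), first to last session spans (4 - 1) x 2 = 6 weeks.
- Participation lasts about 10 weeks, so a pregnancy could also begin after baseline.

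Workload if every relevant participant were screened at baseline and at each sauna visit:

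- Upper bound, as if all 30 could be pregnant: 30 x (1 + 4) = 150.
- If 15 to 20 participants (half to two thirds, an assumption) could be pregnant: 15 x 5 = 75 to 20 x 5 = 100.
- For comparison, COVID-19 rapid tests at the sauna visits: 30 x 4 = 120.

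These figures measure the cost of the change, not the size of the problem. The documents give no number of women, pregnancy rate or test sensitivity, so the number of missed pregnancies cannot be derived.

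**The case against.** The best reply is that silence is not proof. The visit list is mainly an account of participant time, and it is incomplete elsewhere: the SCID needed for inclusion criterion 2 is not named at any visit. A pregnancy test could sit within the baseline screening procedures. This stands, and it rules out a stronger reading that a reader might infer, namely that an unrecognised pregnancy necessarily passes eligibility. The documents show only that it can. The reply does not reach the sauna visits, however, where the condition is written out.

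Second, thinking pregnancy possible is a wider trigger than suspecting it. A woman unaware of a pregnancy may still consider it possible and be screened. This also stands. The gap is limited to those who see no possibility. Criterion 8's bar on intended pregnancy helps with pregnancies that begin after baseline, but not with unintended ones.

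Third, exposure is easily overstated. A reader might infer that every such participant would be heated to 38.5 °C. Half receive sham. That temperature appears in the Background for prior work and the earlier pilot, and no target for this trial's sessions is stated.

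Fourth, how and when to test is a safety decision for the sponsor and IRB, and a conditional screen does not formally contradict the exclusion. That is a fair limit on the remedy. It does not answer the point that the stated rule leaves the exclusion unverified for some participants.

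Finally, the primary analysis plan speaks of outcomes in the past tense, so this pilot may already be complete and an edit may protect no one in it. That affects where the change is made, not whether it is needed.

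**Conclusion.** The point holds in a limited form. Criterion 8 is stated without qualification, the only described screen is conditional on the participant's own view, and no check is named before randomization. A participant with an unrecognised pregnancy who sees no possibility of it can be randomized and, with about a one-in-two chance of active allocation, be heated at up to four sessions over about 6 weeks.

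This rests on two assumptions: that the unitemised baseline procedures contain no pregnancy test, and that the sauna-visit condition is applied as written. If the first is wrong, the eligibility gap closes, but the gap for pregnancies beginning later remains. It is a safety and eligibility matter worth correcting because the correction is cheap. The documents do not support a claim that any ineligible participant was enrolled or that the results are affected.

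**What to change.** Reconcile exclusion 8, the In-Person Screen / Baseline Visit entry and the Sauna Visits 1-4 entry, so that the protocol states how and when pregnancy is ruled out independently of the participant's judgement:

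- In the Sauna Visits 1-4 entry, remove the condition on the existing screen for participants who could be pregnant.
- In the In-Person Screen / Baseline Visit entry, name the check and place it before randomization. If a test is already done there, say so.
- Apply both in the active and sham arms.

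The type of test and its timing are for the sponsor and IRB to set. If this pilot is complete, make the change in the larger trial's protocol and state in the pilot report how criterion 8 was verified.

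The cost is a wording change and at most 150 screens at visits that already take place, with slight participant burden. The unconditional COVID-19 test in the same entry shows that testing before a session already fits the workflow. The documents do not say what the pregnancy screen consists of or costs, so a unit cost cannot be given.
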